ACTG NETWORK COORDINATING CENTER
Social & Scientific Systems, Inc., a DLH Holdings Company
[name]
[name] 20910-3714
[contact]
[contact]

LETTER OF AMENDMENT

DATE: 12 July 2021
TO: ACTG CTU Principal Investigators, CRS Leaders, and CTU/CRS Coordinators
FROM: A5404 Protocol Team
SUBJECT: Letter of Amendment #1 for Protocol A5404

The following information affects the A5404 study and must be forwarded to your institutional review board (IRB)/ethics committee (EC) as soon as possible for their information and review. This Letter of Amendment (LOA) must be approved by your IRB/EC before implementation.

The following information also affects the Sample Informed Consent. Your IRB/EC is responsible for determining the process of informing participants of the contents of this LOA.

Upon receiving final IRB/EC and any other applicable regulatory entity approvals for this LOA, sites should implement the LOA. Sites are still required to submit an LOA registration packet to the DAIDS Protocol Registration Office (PRO) at the Regulatory Support Center along with a Protocol Signature Page, which has been appended to this document. Sites will receive a registration notification for the LOA once the DAIDS PRO verifies that all required LOA registration documents have been received and are complete. An LOA registration notification from the DAIDS PRO is not required prior to implementing the LOA. A copy of the LOA registration notification, along with this letter and any IRB/EC correspondence, should be retained in the site's regulatory file.

The reasons for all of the changes in this LOA are shown in the bulleted list below. Descriptions of the changes themselves begin on page 4 of this document.

- The team revised language requiring participants of ACTIV-2/A5401 to be “at selected sites” to ensure participating A5404 sites can enroll ACTIV-2/A5401 participants from any ACTIV-2/A5401 site.
- The team revised the window for receipt of the mRNA-based COVID-19 vaccine for ACTIV-2/A5401 from 60-240 days to 30-240 days after the last dose of a select ACTIV-2/A5401 investigational therapy.
- The team added the option for participants to enroll after receipt of the first and second doses of community-provided mRNA COVID-19 vaccine.
- The team changed the outcome measures to reflect the time points that will be available for participants who enroll after the second dose of vaccine.

19. "WHAT DO I HAVE TO DO IF I AM IN THIS STUDY?," "Study Visit 8 Weeks (56 days, or about 2 months) after Your First mRNA COVID-19 Vaccine Dose"	17
20. "WHAT DO I HAVE TO DO IF I AM IN THIS STUDY?," "Study Visit 20 Weeks (140 days, or about 5 months) after Your First mRNA COVID-19 Vaccine Dose"	18
21. "WHAT DO I HAVE TO DO IF I AM IN THIS STUDY?," "Additional Study Visit," "At this visit"	18
22. "CAN I CHOOSE THE TYPES OF RESEARCH THAT MY SAMPLES AND INFORMATION ARE USED FOR?"	18
23. "WHY WOULD THE DOCTOR TAKE ME OFF THIS STUDY EARLY?":.....	18
24. "WHAT ARE THE RISKS OF THE STUDY?"	19
25. "ARE THERE RISKS RELATED TO PREGNANCY AND BREASTFEEDING?"	19
26. "WHAT ABOUT CONFIDENTIALITY"	19
27. "WILL I RECEIVE ANY PAYMENT"	20
28. "WHOM TO CONTACT ABOUT THIS STUDY"	20
29. "WHOM TO CONTACT ABOUT THIS STUDY"	21
30. INFORMED CONSENT FORM, SIGNATURE PAGE	22
31. CONSENT FOR USE OF SAMPLES IN OTHER STUDIES	22
SIGNATURE PAGE	26

The following are changes (noted in bold or strikethrough) to A5404, Version 2.0, 07May2021, titled “SARS-CoV-2 Immune Responses after COVID-19 Therapy and Subsequent Vaccine.” These changes will be included in the next version of the A5404 protocol if it is amended at a future date.

1. “At selected sites” was removed from the following sections:
 - a. Schema
 - I. Design section: “Participants of ACTIV-2/A5401 ~~at selected sites~~ who received an investigational therapy or its comparator (placebo or active comparator).”
 - II. Final paragraph of the Sample Size section: “If up to 70 Phase II participants in the A5401/ACTIV-2 trial from each therapy group ~~at selected sites~~ are not able to be enrolled, then Phase III participants in the A5401/ACTIV-2 trial from that select therapy group ~~at selected sites~~ can be enrolled until full enrollment is achieved. However, Phase II participants are preferred.”
 - III. Population section: “ACTIV-2/A5401 trial participants ~~at selected sites~~ who received an investigational therapy or its active comparator/placebo.”
 - b. Study Design
 - I. First bullet of first paragraph: “Participants of ACTIV-2/A5401 who received selected investigational therapy or its comparator (active or placebo) ~~at select sites~~.”
 - II. Fourth paragraph: “If sufficient Phase II participants in the A5401/ACTIV-2 trial from a select therapy group ~~at selected sites~~ are not able to be enrolled, then Phase III participants in the A5401/ACTIV-2 trial from that select therapy group ~~at selected sites~~ can be enrolled until full enrollment is achieved. However, Phase II participants are preferred.”
 - c. Section 4.1.3: “For participants who are in, or who have completed, the ACTIV-2/A5401 trial: Receipt of all selected investigational therapy or active comparator/placebo for that therapy ~~at selected sites~~.”
2. Window for receipt of mRNA-based COVID-19 vaccine for ACTIV-2/A5401 participants

The window for receipt of the mRNA-based COVID-19 vaccine for ACTIV-2/A5401 participants was changed from 60-240 days to **30-240** days after their last dose of a select ACTIV-2/A5401 investigational therapy. This change is reflected in the following sections:

- a. Schema, Design Section
The second sentence of the third paragraph: “Participants in ACTIV-2/A5401 will receive their mRNA-based COVID-19 vaccine ~~6030~~-240 days after receiving their last dose of a select ACTIV-2/A5401 investigational therapy, or its comparator.”
- b. Section 2.2 Rationale, sub-section Reinfection
The third sentence of the second paragraph: “The optimal timing of a vaccination to boost such waning immunity is unknown and is the rationale for the ~~6030~~-240-day window after receiving their last dose of ACTIV-2/A5401 select therapy (i.e., post-infection) for vaccination in the proposed study.”

c. Section 3.0 Study Design

I. The second sentence of the second paragraph, "ACTIV-2/A5401 participants will be offered the Moderna mRNA-1273 COVID-19 vaccine or receive an mRNA-based COVID-19 vaccine in the community **60**30-240 days after receiving their last dose of ACTIV-2/A5401 select therapy (investigational agent or active comparator or placebo)."

II. Figure 3.0-1 was replaced with the figure below:

[figure not shown]

Figure 3.0-1: This schema includes common assessments for ACTIV-2/A5401 participants in both phases 2 and 3 (panel A). If possible, blood will be collected before each vaccine dose is administered and 56, 140, 365, and 730 days after **their first vaccine dose** (panel B). If possible, participants will be contacted 7 days after each vaccine dose to grade vaccine-associated symptoms.

d. Section 4.1 Inclusion Criteria

I. Section 4.1.4: "For participants who are in, or who have completed, the ACTIV-2/A5401 trial and will be receiving study-provided Moderna mRNA-1273 COVID-19 vaccine: Receipt of the last dose of investigational therapy or active comparator/placebo for that therapy ≥ 30 60 days and ≤ 240 days prior to study entry."

II. Section 4.1.5 (with an additional revision to clarify that this applies to participants who have already received one or both vaccine doses): "For participants who are in, or who have completed, the ACTIV-2/A5401 trial and **have received or** will be receiving community-provided mRNA-based COVID-19 vaccine: Receipt of the last dose of investigational therapy or active comparator/placebo for that therapy ≥ 30 and ≤ 240 days prior to **receipt or** planned receipt of the first dose of community-provided vaccine."

e. Section 6.2.2 Entry Evaluations

The fourth paragraph of this section was revised to, “ACTIV-2/A5401 participants are expected to receive the first dose of study vaccine **3060**-240 days after receiving the last dose of an investigational therapy or corresponding active comparator/placebo in ACTIV-2/A5401.”

3. Participants will be able to enroll after receiving both doses of their mRNA-based COVID-19 vaccine in the community. The following sections have been revised accordingly:

a. Schema, Design Section

The fourth paragraph of this section was revised as follows: “All participants will have blood collected and immune responses measured before first vaccine dose (if feasible), at second dose of vaccine (e.g., 28 days later; **if feasible**), and at 56 (**if feasible**), 140, 365, and 730 days after **their first vaccine dose**.”

b. Schema, Regimen

ACTIV-2/A5401 participants

Participants will receive the following study-provided regimen: Moderna mRNA-1273 COVID-19 vaccine, 100 µg (0.5 mL) to be administered intramuscularly (IM) at Entry and Day 28.

Or

Participants will receive a two-dose series of a community-provided mRNA-based COVID-19 vaccine that has received FDA EUA or FDA approval (e.g., Moderna or Pfizer). Vaccine will not be provided by the study.

NOTE: These participants may enter the study before their first vaccine dose, after their first vaccine dose, or after their second vaccine dose.

Or

Participants will receive their first Moderna mRNA-1273 COVID-19 vaccine dose in the community. Their second Moderna mRNA-1273 dose will be provided by the study (100 µg [0.5 mL] to be administered IM 28 days after their first dose).

NOTE: These participants may enter the study before or after their first vaccine dose.

Participants without prior history of SARS-CoV-2 infection

Participants will receive the following study-provided regimen: Moderna mRNA-1273 COVID-19 vaccine, 100 µg (0.5 mL) to be administered IM at Entry and Day 28.

c. Section 3.0 Study Design

The last sentence of the second paragraph: “Participants will have blood collected and immune responses measured before the first vaccine dose (if feasible), and before the second dose of vaccine (e.g., 28 days later for Moderna vaccine and 21 days later for Pfizer vaccine if given in the community) (**if feasible**), and 56 (**if feasible**), 140, 365, and 730 days after **their first vaccine dose** (Figure 3.0-1).”

d. Section 4.2 Exclusion Criterion 4.2.2

This criterion was revised as follows: “For participants who are in, or who have completed, the ACTIV-2/A5401 trial: Self-report of receipt of the ~~second~~ **first** dose of an mRNA-based COVID-19 vaccine **140 days or more before A5404 enrollment.**”

e. Section 5.1.1 Regimen and Duration

Participants will receive the following study-provided regimen: Moderna mRNA-1273 COVID-19 vaccine, 100 µg (0.5 mL) to be administered intramuscularly (IM) at **Entry** and Day 28.

Or

Participants will receive a two-dose series of a community-provided mRNA-based COVID-19 vaccine that has received FDA EUA or FDA approval.

NOTE: Participants who receive a community-provided mRNA-based COVID-19 vaccine may receive their **first and second** COVID-19 vaccine dose(s) before study entry.

Or

Participants will receive (or have recently received) a community-provided Moderna mRNA-1273 COVID-19 vaccine at (or before) **Entry** and study-provided Moderna mRNA-1273 COVID-19 vaccine, 100 µg (0.5 mL) to be administered intramuscularly (IM) at at least 28 days apart.

f. Section 6.1, Table 6.1-3

The title of this section was changed to, “~~Community Provided mRNA-based COVID-19 Vaccine~~ Schedule of Evaluations for ACTIV-2/A5401 Participants **who Received First Dose of a Community-Provided mRNA-based COVID-19 Vaccine Before Entry or Will Receive First Dose After Entry**”

g. Section 6.1, Table 6.1-4 was added:

Table 6.1-4. Schedule of Evaluations for ACTIV-2/A5401 Participants Who Received First and Second Doses of a Community-Provided mRNA-based COVID-19 Vaccine before Entry

Evaluation	Screening See section 6.2.1	Study Entry See section 6.2.2	56 Days Post-Vaccination #1 See section 6.2.3	140 Days Post-Vaccination #1 See section 6.2.3	365 Days (1 Year) Post-Vaccination #1	730 Days (2 Years) Post-Vaccination #1	Premature Study D/C	Event-Driven Evaluation: SARS-CoV-2 Infection
Visit Window (days)	-28		+7	±7	±28			+14
Visit Type (P: In Person, R: Remote)	R/P	P	P	P	P	P	P	P
Documentation of ACTIV-2/A5401 participation and receipt of investigational therapy or active comparator/placebo for investigational therapy	X							
Medical/Medication History	X	X						
Clinical Assessments	X	X	X	X	X	X	X	X
Pregnancy Testing		X	If pregnancy suspected				X	X
Documentation of Community-Provided COVID-19 Vaccination (see section 6.3.7)		X						
Vaccine Symptom Screen (see section 6.3.8)		X						
Stored Plasma		X	X	X	X	X	X	X
Stored Serum		X	X	X	X	X	X	X
Stored PBMCs		X	X	X	X	X	X	X
Stored PAXgene RNA Tube		X						
Documentation of New Active SARS-CoV-2 Infection by Antigen or Nucleic Acid Test								X
Nasopharyngeal (NP) Swab Collection (See section 6.3.11)								X
ACTIV-2/A5401 Investigational Therapy or Active Comparator/Placebo Questionnaire		X						

h. Section 6.2.1 Screening Evaluations

I. The second paragraph has been revised to, “If the participant is receiving community-provided mRNA COVID-19 vaccine, then screening evaluations must occur prior to the participant receiving their second dose of vaccine; however, it is preferred for these participants to have their screening evaluations before their first or their second vaccine dose, if feasible.”

i. Section 6.2.2 Entry Evaluations

I. The header for the last paragraph was revised to, “Entry Evaluations for ACTIV-2/A5401 Participants who Received First Dose of a Community-Provided mRNA-based COVID-19 Vaccine Before Entry or Will Receive First Dose After Entry”

j. Section 6.2.3 Post-Entry Evaluations

I. The header, Community-Provided Vaccine: Day of Second Dose of Vaccine sub-section was revised to include the following as the first paragraph: “**This visit will only be performed if the participant enters the study before their second vaccine dose.**”

II. The following sub-section was added after the Community-Provided Vaccine: Day of Second Dose of Vaccine sub-section.

56 and 140 Days Post-Vaccination #1 for ACTIV-2/A5401 Participants Who Received First and Second Doses of a Community-Provided mRNA-based COVID-19 Vaccine before Entry

- **56 days post-vaccination #1 timepoint:**
 - This visit will not be conducted if the participant enrolls more than 56 days after their first vaccine dose.
 - This visit may be combined with the Entry visit if the participant enrolls between 56 and 63 days after their first mRNA COVID-19 vaccine dose. Evaluations indicated at both timepoints will be conducted only once.
- **140 days post-vaccination #1 timepoint:** This visit may be combined with the Entry visit if the participant enrolls between 133 and 147 days after their first mRNA COVID-19 vaccine dose. Evaluations indicated at both timepoints will be conducted only once.

k. Section 6.3.7 Vaccine Administration

The first sub-section title was changed to, “Documentation of Community-Provided COVID-19 Vaccination”

l. Section 6.3.8 Vaccine Symptom Screen

The first sentence has been revised to, “For participants who receive community-provided mRNA-based COVID-19 vaccine: If the participant enrolls >14 days after the first or second dose of their vaccine, then a Vaccine Symptom Screen is not collected for the doses provided prior to enrollment.”

4. Section 4.1, Inclusion Criterion 4.1.3:

The following note was added.

NOTES:

- Selected investigational therapies will be posted on the A5404 PSWP.
- **For participants who received camostat or the active comparator/placebo for camostat: Receipt of ≥50% of the doses indicated in ACTIV-2/A5401.**

5. Section 5.2, Study Product Formulation and Preparation**a. In section 5.2.1 Formulation and Storage, the following modifications have been made:**

The Moderna mRNA-1273 COVID-19 vaccine is supplied as a frozen suspension, stored between ~~-25-50°~~ to -15°C, in multi-dose vials, and does not contain a preservative. ~~Store in the original carton to p~~ **Protect** from light. Do not store on dry ice or below ~~-40-50°C~~. The Moderna mRNA-1273 COVID-19 vaccine is white to off-white suspension. It may contain white or translucent product-related particulates.

The Moderna mRNA-1273 COVID-19 vaccine must be thawed prior to administration. After thawing, a maximum of 10-11 doses (0.5 mL each) can be withdrawn from each vial, dependent on the syringes and needles used. Vials can be stored refrigerated between 2° to 8°C for up to 30 days prior to first use. Do not refreeze once thawed. Unpunctured vials may be stored between 8° to 25°C for up to ~~42~~ **24** hours. Do not refreeze. After the first dose has been withdrawn, the vial should be held between 2° to 25°C and discarded after ~~6~~ **12** hours. Do not refreeze.

b. In section 5.2.2 Preparation, the following modifications have been made:

1. Remove one vial of the Moderna mRNA-1273 COVID-19 vaccine from the freezer and thaw either in the refrigerator or at room temperature. If thawed in the refrigerator, the vial must be kept between 2°C and 8°C for two hours and 30 minutes. If thawed at room temperature, the vial must be kept between 15°C and 25°C for one hour. Once thawed, the vial may be kept between 8°C and 25 °C for up to ~~42~~ **24** hours. Do NOT refreeze.
2. With the vial upright, gently swirl the vaccine. Do NOT shake. Do NOT dilute the vaccine.
3. Examine the vaccine. It should be white to off-white in color and may contain white or translucent product-related particulates. Do not use if liquid contains other particulate matter or is discolored.
4. Withdraw 0.5 mL of vaccine into an appropriately sized syringe. When the stopper of the vial is punctured to start preparation, record this as the vaccine preparation time. Assign a ~~6~~ **12** hour beyond use date and time from the preparation time.

The prepared vaccine should be administered immediately. If immediate administration is not possible, the **prepared** vaccine may be stored ~~refrigerated at between 2°C to 8°C or left at ambient room temperature at 15°C to and~~ 25°C for up to ~~6~~ **12** hours. **Keep out of direct sunlight.**

6. Section 6.1 Schedule of Evaluations:

The windows for screening for the following groups have been changed to 28 days before study entry. Day 0 has been removed from the Study Entry header for clarity and

consistency. Tables 6.1-1, 6.1-2, and 6.1-3 have been revised accordingly. Additionally, Table 6.1-2 was updated to indicate that stored PBMCs for 35 total SARS-CoV-2-naïve participants are to be collected at the Event-Driven Evaluation: SARS-CoV-2 Infection visit. The changes are shown below.

Table 6.1-1. Study-Provided Moderna COVID-19 Vaccine Schedule of Evaluations for ACTIV-2/A5401 Participants

Evaluation	Screening	Study Entry/Day 0 See section 6.2.2	Post-Vaccination #1 Follow-up/Day 7	Day 28	Post-Vaccination #2 Follow-up/Day 35	Day 56	Day 140	Day 365 (1 Year)	Day 730 (2 Years)	Premature Study D/C	Event-Driven Evaluation: SARS-CoV-2 Infection
Visit Window (days)	-28	7-14 days post-vaccine	+7	7-14 days post-vaccine	+7	±7	±28			+14	

Table 6.1-2. Study-Provided Moderna COVID-19 Vaccine Schedule of Evaluations for Participants without Prior History of SARS-CoV-2 Infection

Evaluation	Screening	Study Entry/Day 0 See section 6.2.2	Post-Vaccination #1 Follow-up/Day 7	Day 28	Post-Vaccination #2 Follow-up/Day 35	Day 56	Day 140	Day 365 (1 Year)	Day 730 (2 Years)	Premature Study D/C	Event-Driven Evaluation: SARS-CoV-2 Infection
Visit Window (days)	-28	7-14 days post-vaccine	+7	7-14 days post-vaccine	+7	±7	±28			+14	
Visit Type (P: In Person, R: Remote)	R/P	P	R	P	R	P	P	P	P	P	P
Stored PBMCs for 35 total SARS-CoV-2-naïve participants (See section 6.3.9)		X				X		X	X		X

Table 6.1-3. Community Provided mRNA-based COVID-19 Vaccine Schedule of Evaluations for ACTIV-2/A5401 Participants who Received First Dose of a Community-Provided mRNA-based COVID-19 Vaccine Before Entry or Will Receive First Dose After Entry

Evaluation	Screening See section 6.2.1	Study Entry/Day 0 See section 6.2.2	Post-Vaccination #1 Follow-up See section 6.2.3	Day of 2 nd dose of vaccine	Post-Vaccination #2 Follow-up	56 Days Post-Vaccination #1	140 Days Post-Vaccination #1	365 Days (1 Year) Post-Vaccination #1	730 Days (2 Years) Post-Vaccination #1	Premature Study D/C	Event-Driven Evaluation: SARS-CoV-2 Infection
Visit Window (days)	-28		7-14 days post-1 st dose of vaccine	-3	7-14 days post-2 nd dose of vaccine	+7	±7	±28			+14

7. Section 6.2 Timing of Evaluations, has been revised to reflect that the windows for screening for all groups has been changed to 28 days before study entry.

- The third and fourth paragraphs of section 6.2.1, Screening Evaluations have been changed as follows.

For **all** participants ~~receiving study provided vaccine~~, screening evaluations to determine eligibility must be completed within **28** days prior to study entry unless otherwise specified.

~~For participants receiving community provided vaccine, screening evaluations to determine eligibility must be completed within 14 days prior to study entry unless otherwise specified.~~

- The first and second paragraphs of section 6.2.2, Entry Evaluations have been changed as follows.

For **all** participants ~~receiving study provided vaccine~~, entry evaluations must occur **≤28** days after screening evaluations unless otherwise specified.

~~For participants receiving community provided vaccine, entry evaluations must occur **≤14** days after screening evaluations unless otherwise specified.~~

8. Section 7.4 Study Monitoring. The second sentence of the third paragraph was revised as follows.

The first interim review will occur when 10 participants have enrolled to one select therapy group, **received their first dose of vaccine after study entry**, and their data through study Day 7 (7 days after the first vaccine dose) are available, or 3 months after the first

participant enrolls, whichever occurs first.

9. Section 10.0 Statistical Considerations was revised as follows.

- a. Section 10.2.1.1 (Primary Outcome Measure)
“Neutralizing antibody (NAb) level at least **140** days after the first dose of the study- or community-provided vaccine.”
- b. Section 10.2.2.2 (Secondary Outcome Measure)
“New Grade 3 or higher AE, or SAE, or AE leading to change or discontinuation in vaccine receipt from first dose of the mRNA-based COVID-19 vaccine and through **140** days after the first dose of vaccine.”
- c. Section 10.2.2.6 (Secondary Outcome Measure)
“Flow cytometry of PBMC for markers of exhaustion on B and T cells at study entry/Day 0, 56 **and 140** days after the first vaccine dose.”
- d. Section 10.4 Sample Size. The first sentence of the third paragraph was revised.

For the primary outcome measure of NAb levels **56 140** days after the first vaccine dose, we will calculate the ratio of geometric mean responses (GMRs) for participants with prior select investigational therapy exposure versus participants who received placebo.

e. Section 10.6 Analyses.

I. The first sentence of the fifth paragraph was revised.

The primary analysis population will include all participants who received at least one vaccine dose and provided NAb responses at least **56 140** days after the first vaccine dose.

II. The first sentence of the sixth paragraph was revised.

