3.2 Secondary Outcome Measures

- 3.2.1** Relative pre-vaccine to post-vaccine change in NAb response defined as the ratio of post-vaccine level/pre-vaccine level. The pre-vaccine NAb measurement will be obtained before the first dose of the vaccine and the post-vaccine measurement will be obtained at least 56 days after the first dose of the vaccine. (Objective 2.3.1.1)
- 3.2.2** New Grade 3 or higher AE, or SAE, or AE leading to change or discontinuation in vaccine receipt from first dose of the mRNA-based COVID-19 vaccine and through 140 days after the first dose of vaccine. (Objective 2.3.2.1)
- 3.2.3** Grade 1 or higher allergic reaction from first dose of the mRNA-based COVID-19 vaccine through the visit 56 days after the first dose of the vaccine. (Objective 2.3.2.1)
- 3.2.4** Grade 2 or higher injection site reaction from first dose of the mRNA-based COVID-19 vaccine through the visit 56 days after the first dose of the vaccine. (Objective 2.3.2.1)
- 3.2.5** Relative pre-vaccine to post-vaccine change in NAb response defined as the ratio of post-vaccine level/pre-vaccine level by received vaccine, i.e., Moderna versus Pfizer. The pre-vaccine NAb measurement will be obtained before the first dose of the vaccine, and the post-vaccine measurement will be obtained at least 56 days after the first dose of the vaccine. (Objective 2.3.1.1)

4 General Considerations

The aim of this study is to describe immunologic responses to mRNA-based SARS-CoV-2 vaccine among individuals who previously received investigational therapy in ACTIV-2/A5401 for SARS-CoV-2 infection in comparison to individuals who received a placebo. As ACTIV-2/A5401 is expected to change from using a placebo control to an active control, this study's aim will also evolve to describe immunologic responses to mRNA-based SARS-CoV-2 vaccine among individuals who previously received investigational therapy in ACTIV-2/A5401 for SARS-CoV-2 infection in comparison to individuals who received an active control.

Estimates and confidence intervals for NAb will be obtained by using a log base 10 transformation on the PSV values, then using linear regression with an indicator variable for prior select COVID-19 therapy exposure versus placebo using standard methods, assuming that the \log_{10} NAb responses are approximately normally distributed within exposure group.

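### Section 6.3.8 does not say whether its 14-day test applies to each dose separately; read literally, it leaves the Entry symptom screen in Table 6.1-4 with no participant to apply to

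*Protocol*

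**What the plan says.** - **The rule.** Letter of Amendment #1 (LOA #1), item 3l, revises the first sentence of Section 6.3.8 for recipients of community vaccine: "If the participant enrolls >14 days after the first or second dose of their vaccine, then a Vaccine Symptom Screen is not collected". The sentence ends with its scope, which is plural: "for the doses provided prior to enrollment". The other sentences of 6.3.8 are not reproduced.
- **The schedule.** Item 3g of the same letter adds Table 6.1-4 for "Participants Who Received First and Second Doses of a Community-Provided mRNA-based COVID-19 Vaccine before Entry". Its row "Vaccine Symptom Screen (see section 6.3.8" is marked at Study Entry only. The row names no dose and sends the reader back to 6.3.8.
- **The dose interval.** Section 3.0, as revised by item 3c, places the second dose "28 days later for Moderna vaccine and 21 days later for Pfizer vaccine if given in the community".
- **Latest entry.** Exclusion criterion 4.2.2, as revised by item 3d, bars anyone whose first dose was "140 days or more before A5404 enrollment".
- **Symptom follow-up elsewhere.** The Figure 3.0-1 legend says that, if possible, "participants will be contacted 7 days after each vaccine dose to grade vaccine-associated symptoms". Table 6.1-3 has a separate 7-14 day follow-up window after each dose.
- **The outcomes served.** SAP 3.2.4 is "Grade 2 or higher injection site reaction from first dose of the mRNA-based COVID-19 vaccine through the visit 56 days after the first dose". SAP 3.2.3 covers Grade 1 or higher allergic reactions over the same period.

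**The concern.** The rule has one trigger, either dose being more than 14 days old, and one consequence that covers every dose given before enrollment. It does not limit the consequence to the dose that is out of window. A participant who enters a few days after dose 2 is still several weeks past dose 1. On the literal wording, that person is not asked about dose 2 either.

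The same letter schedules a symptom screen at Entry for this very group. A site reading only 6.3.8 could skip the screen for all of them. A site reading Table 6.1-4 could do it for those close to dose 2. At stake is whether second-dose allergic and injection-site reactions are collected consistently from two-dose entrants, and so how complete the data are for two secondary safety outcomes in a small study.

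**Working it through.** The plan states no figure on this point, so there is nothing to reproduce. The check is to list every possible entry day and see when a screen survives.

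**Inputs.** Dose interval g = 21 days (Pfizer) or 28 days (Moderna), from Section 3.0. Window = 14 days, from Section 6.3.8. Last eligible entry day = 139 days after dose 1, from criterion 4.2.2. I assume that actual intervals equal the planned ones.

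**Notation.** Let d be the entry day counted from dose 1. A two-dose entrant has d from g to 139, and enters d − g days after dose 2.

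**Reading A (literal).** The screen is kept only if neither dose is out of window: d ≤ 14 and d − g ≤ 14.

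**Reading B (dose by dose).** The dose-1 screen is kept if d ≤ 14. The dose-2 screen is kept if d − g ≤ 14.

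| | Pfizer, g = 21 | Moderna, g = 28 |
|---|---|---|
| Possible entry days | 139 − 21 + 1 = 119 | 139 − 28 + 1 = 112 |
| Reading A: days with any screen | 0 | 0 |
| Reading B: days with dose-1 screen | 0 | 0 |
| Reading B: days with dose-2 screen | d = 21 to 35, 15 days | d = 28 to 42, 15 days |

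**Dependence on the interval.** Under Reading A a screen needs d ≤ 14, and d is at least g, so g must be 14 or less. At g = 15 or more the count is zero. The planned intervals exceed 14 by 7 and 14 days, so modest departures from schedule do not change the result.

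**Relevance to the SAP outcomes.** The entry days on which the readings differ (21-35 or 28-42) all come before day 56. Second-dose reactions in these entrants therefore fall inside the period defined in SAP 3.2.3 and 3.2.4.

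**Who is not affected.** For someone entering after dose 1 but before dose 2, only one dose precedes enrollment, and the two readings give the same answer. The ambiguity is confined to Table 6.1-4 participants entering 0 to 14 days after dose 2.

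**Which reading fits the other text.** Dose 1 is out of window for every Table 6.1-4 participant, so the Entry mark can serve only dose 2, and only under Reading B. The Figure 3.0-1 legend and Table 6.1-3 also treat the doses separately. The table does not say this itself; it has to be inferred.

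**The case against.** The strongest reply is that the dose-by-dose reading is the sensible one. It gives the Table 6.1-4 entry a use and agrees with the figure legend and Table 6.1-3, so a careful site would follow it. That stands. A reader might infer that every two-dose entrant lost the second-dose screen. The documents do not support this as fact: it follows from the literal reading alone, and nothing shows what sites did.

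Two further cautions stand. Only the first sentence of 6.3.8 is supplied, and the rest may settle the matter. Item 3l also shows no revision marks, while other items in the letter run old and new text together, so the exact wording could be affected by extraction. That is a possibility only; the sentence is complete as it reads.

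A reader might also infer that reaction proportions in the previously infected groups are biased downward against the naive cohort. The documents do not establish this:

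- The missing-data rule in SAP 5.3 covers participants who discontinue follow-up. It does not say how a dose that was never screened is counted.
- SAP 7.6 limits its reaction summaries to post-entry events, whereas 5.3 and 7.9 count from the first dose. Whether a pre-entry reaction enters the results is therefore itself unclear.
- Table 6.1-4 also schedules Clinical Assessments at Entry and later visits, and Medical/Medication History at Entry. Their content is not supplied, so the screen cannot be called the only source of reaction data.
- SAP 5.3 plans separate proportions with exact intervals and no test between groups.

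Finally, the gain from a clearer rule is limited. Dose 1 stays unscreened for two-dose entrants on either reading, and dose 2 is recoverable on 15 of 112 to 119 entry days. Accrual closed on February 25, 2022, so rewording recovers no data. This limits the size of the point but does not remove the inconsistency.

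**Conclusion.** The point holds as an internal inconsistency. Read literally, 6.3.8 leaves the Entry screen in Table 6.1-4 with no one to apply to at any dose interval of 15 days or more. Read dose by dose, it keeps the second-dose screen for entry 0 to 14 days after dose 2. The supplied text does not choose between them, so collection may have differed between sites, and ascertainment for SAP 3.2.3 and 3.2.4 may be incomplete or uneven.

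The size in participants or events cannot be computed. SAP 2.4 gives 43 enrolled in total, but not how many entered after dose 2 or when. The 15 days are calendar days on which entry was possible, not a share of participants. No direction of bias is claimed. The conclusion rests on the planned intervals and on the one supplied sentence of 6.3.8.

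**What to change.** 1. **Reconcile 6.3.8 with Table 6.1-4** by applying the existing 14-day test to each dose. Suggested wording: *The screen is not collected for a community dose given more than 14 days before enrollment; it is collected for each community dose given 14 days or less before enrollment.* The cost is one sentence. The Entry screen is already scheduled, so no visit or procedure is added.
2. **Report what was collected.** Because accrual has closed, state how many participants entered after both doses and, for each dose, how many were screened. The cost is one small table from existing records.
3. **Do not count unscreened doses as observed non-events** for allergic and injection-site reactions. Show them as not ascertained, alongside the proportions in SAP 5.3 and 7.9. The SAP says that the final analysis report was conducted under version 3.0, so items 2 and 3 may need to go into an addendum or a note to the published tables.
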